7.9.1.2. Sensitivity Analyses

7.9.1.2.1. MMRM Analysis of Primary Outcome

An MMRM analysis will be used to assess the difference between treatment groups in change from baseline for the PACC score at 240 weeks (Visit 66). Change from baseline at each visit when the composite score is scheduled will be the dependent variable. Visit will be treated as a categorical variable with values equal to the visit numbers at which the composite measure was scheduled. We will assume an unstructured covariance structure. The model for the fixed effects will include the following terms: (i) baseline PACC score, (ii) treatment, (iii) visit, (iv) treatment-by-visit interaction, (v) age, (vi) education, (vii) APOE4 Carrier Status (yes/no), and (viii) baseline florbetapir cortical SUVr.

The null hypothesis is that the treatment difference between solanezumab and placebo for the PACC score at 240 weeks is equal to zero. The primary analysis will be carried out in the mITT population that is randomized and has a baseline score and at least 1 post-baseline assessment. If the unstructured covariance structure matrix results in a lack of convergence, the same sequence of covariance structures as above will be attempted. Additionally, a Bayesian disease progression model (DPM) (Sparks 2021) with a proportional treatment effect will be conducted to assess statistical differences in the rate of decline of the PACC score between the solanezumab group and the placebo group. The analysis is testing the hypothesis that the disease progression ratio (DPR), defined as the ratio of the rate of decline of the solanezumab arm divided by the rate of decline of the placebo arm, is less than 1.

$$H_0: DPR=1$$

$$H_1: DPR<1$$

The key assumption of the DPM is that it assumes that the treatment effect of solanezumab is proportional to placebo over the course of the study. The proportionality assumption is similar to the assumption made in proportional hazards modeling of time to event data. The model includes diffuse priors on all parameters; therefore, the prior distributions have very little impact on the posterior distributions. No information or knowledge of the effect of solanezumab from previous studies will be incorporated into the prior distributions.

The DPM is as follows:

$$Y_{ij} = \gamma_i + e^{\theta T_i} \sum_{v=0}^j \alpha_v + \varepsilon_{ij}$$

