where Y_{ij} denotes the PACC score at visit j for participant i ; the PACC score for a participant at baseline (prior to treatment) is Y_{i0} . The value γ_i ($i=1, 2, \dots, k$) represents a participant specific random effect. The parameter T_i denotes the treatment arm for participant i , where T_i has a value

of 1 if a participant is randomized to solanezumab, and a value of 0 if the participant is randomized to placebo. The parameter α_v is the change in mean PACC score for placebo from visit $v-1$ to v , and ε_{ij} is the error term. The DPR for solanezumab relative to placebo is provided by the parameter e^θ . Covariates of the model include PACC test version, age at baseline, education, APOE4 Carrier Status (yes/no), and baseline florbetapir cortical SUV_r.

To examine the hypothesis of a disease progression benefit, we calculate the posterior probability of the alternative hypothesis for various thresholds (for example, 0% slowing, 25% slowing relative to placebo, etc.). A 95% credible interval (from the 2.5th to the 97.5th percentiles) and posterior mean and median disease progression ratio will be presented.

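### As printed, the disease progression model multiplies a baseline term, and not only the decline, by the treatment ratio; whether this matters depends on details the SAP leaves open

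*SAP*

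**What the plan says.** SAP 7.9.1.2.1 gives the model as Y_ij = γ_i + exp(θT_i)·Σ_{v=0..j} α_v + ε_ij, where T_i is 1 for solanezumab and 0 for placebo. Its terms are described as follows.

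- Visit 0 is a modelled outcome: "the PACC score for a participant at baseline (prior to treatment) is" Y_i0.
- α_v "is the change in mean PACC score for placebo from visit" v−1 to v.
- γ_i "represents a participant specific random effect". Its mean and distribution are not given, and no separate intercept is written.
- The disease progression ratio (DPR) is "defined as the ratio of the rate of decline of the solanezumab arm divided by the rate of decline of the placebo arm". "The DPR for solanezumab relative to placebo is provided by the parameter" exp(θ).
- "The model includes diffuse priors on all parameters", and the section adds that the priors therefore hardly affect the posterior.
- "Covariates of the model include PACC test version, age at baseline, education", APOE4 carrier status and baseline SUVr. They are not shown in the equation, and centring is not mentioned.

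SAP 5.1 scores the PACC by subtracting each component's baseline mean and dividing by its baseline SD. Protocol 10.1.1 mentions only the division.

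**The concern.** At baseline (j = 0) the printed mean is γ_i + α_0 on placebo and γ_i + exp(θ)·α_0 on solanezumab. No visit precedes baseline, so the SAP's definition of α_v gives α_0 no meaning, and nothing sets it to zero. If it is estimated, one parameter has to describe both a baseline gap between randomised arms and the ratio of decline. That departs from the SAP's own definition of the DPR. It also drops the equal-baseline constraint that SAP 7.9.1.1 imposes on the primary model.

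At stake are the DPR estimate, its credible interval and the posterior probabilities of slowing, all of which the SAP says will be reported.

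**Working it through.** The documents give no numerical result for the DPM, so there is none to reproduce.

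**Inputs from the documents.** 575 per arm; 11 PACC visits from week 0 to week 240; SD of change 2.85 (SAP 6.2). The placebo decline is not stated. I use 2.13, the ADNI amyloid-group difference in SAP 6.2, with a range of 1.0 to 2.66.

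**Assumptions.** True DPR 0.75 (the SAP's 25% slowing example), linear decline, complete data, random intercept, baseline SD 2.8. The residual variance is then 2.85²/2 = 4.06 and the participant variance 2.8² − 4.06 = 3.78.

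**Step 1: algebra.** The printed gap between arms at visit j is (exp(θ) − 1)·(α_0 + D_j), where D_j is the placebo change to visit j. The intended gap is (exp(θ) − 1)·D_j. Take exp(θ) = 0.75 and α_0 = +5:

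- At baseline the formula gives −0.25 × 5 = −1.25, where randomisation implies 0.
- At week 240 it gives −0.25 × (5 − 2.13) = −0.72, where the true gap is −0.25 × (−2.13) = +0.53.

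The fit can then reconcile the two only by moving exp(θ). With α_0 = 0 the two expressions are identical.

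**Step 2: γ_i with mean zero, large-sample maximum likelihood, no covariates, decline 2.13.**

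| Baseline intercept | DPR as printed | DPR, sum from v = 1 |
|---|---|---|
| −5 | 0.933 | 0.750 |
| −2 | 0.859 | 0.750 |
| −0.5 | 0.777 | 0.750 |
| 0 | 0.750 | 0.750 |
| +0.5 | 0.738 | 0.750 |
| +2 | 0.845 | 0.750 |
| +5 | 0.998 | 0.750 |
| +10 | 1.015 | 0.750 |

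The pull is stronger with a smaller decline (1.0: 0.985 at +2, 1.015 at +5) and weaker with a larger one (2.66: 0.803 and 0.977). A larger participant variance (about 8) also weakens it, at decline 2.13: 0.744 at +0.5, 0.803 at +2, 0.954 at +5 and about 1.00 at +10.

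**Step 3: where a non-zero intercept could come from.** SAP scoring makes the overall baseline PACC mean zero. Simulated trials (60 per setting, decline 2.13) gave a mean DPR as printed of 0.741 without covariates and 0.752 with centred covariates. For uncentred covariates I assumed means of 72 years (age), 16.5 years (education) and 1.33 (SUVr):

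- Coefficients −0.12, 0.15 and −1.0 imply an intercept of 8.64 − 2.475 + 1.33 = +7.5. Mean DPR 1.002, with 90% of trials at or above 1.
- Age coefficient −0.05 instead implies 3.6 − 2.475 + 1.33 = +2.5. Mean DPR 0.742.
- Education only implies −2.5. Mean DPR 0.784.

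With the sum from v = 1 and the first set of coefficients, the mean was 0.745 and no trial reached 1. The results therefore depend heavily on coefficients that the documents do not give.

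**Step 4: γ_i with a free mean.** The likelihood estimate is then sound (0.746 with the first set of uncentred coefficients), because α_0 = 0 fits the truth. But as θ approaches 0, a very large α_0 mimics a constant gap between arms, so diffuse priors place posterior mass near DPR = 1. A Bayesian fit used no covariates, known variances, a N(0,1) prior on θ and 100 trials. The share of trials with P(DPR < 1) above 0.975 was:

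| Decline | Sum from v = 1 | Printed, prior SD 10 | SD 100 | SD 1000 |
|---|---|---|---|---|
| 1.0 | 88% | 52% | 33% | 24% |
| 1.5 | 98% | 92% | 83% | 74% |
| 2.13 | 100% | 100% | 96% | 96% |

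The prior SD applies to the mean parameters, including α_0. The corrected model gave the same result at all three prior scales. Two further runs at decline 1.0 agree in direction: 400 trials gave 83% against 57%, 40% and 32%, and 30 trials at prior SD 1000 gave 90% against 23%.

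**The case against.** The strongest reply is that this is loose notation. SAP 5.1 centres the PACC, and scaling a zero baseline mean changes nothing. γ_i is not said to have mean zero, so it can carry the baseline level. A change from a visit before baseline is naturally read as zero, and the DPR is defined on decline alone. The published source cited for the model may settle the matter, but it is not available here. The DPM is also one sensitivity analysis: SAP 7.4 makes the spline analysis primary, and no decision rule uses the DPR.

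Most of this stands. A reader might infer that the printed formula generally biases the DPR toward 1, or that a working drug would be read as accelerating decline. The documents do not support either. At a zero intercept there is no shift, at +0.5 the ratio moves slightly away from 1, and values above 1 need a large positive intercept and then exceed it only marginally.

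The free-mean reading is not a complete answer, however. It removes the likelihood bias but leaves the trade-off between α_0 and θ in Step 4. That sits badly with the SAP's statement that the priors matter little.

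**Conclusion.** The printed formula contradicts the SAP's own definitions of α_v and of the DPR, and it allows the randomised arms to differ at baseline. The consequence is conditional:

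- **SAP scoring, centred covariates, mean-zero γ_i:** negligible.
- **Mean-zero γ_i, intercept well away from zero** (possible with uncentred age, education or SUVr, depending on their coefficients): a true 0.75 can be pulled toward 1, or marginally past it for a large positive intercept.
- **Free mean for γ_i:** diffuse priors lower the posterior probability of slowing when decline is modest. The loss is large at an assumed decline of 1.0 and small at 2.13.

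These sizes rest on the assumed declines, variances, coefficients and prior scales shown, and are not predictions for this trial. The primary spline test is unaffected. The point should be corrected because the DPR results will be reported and an analyst could code the formula literally.

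**What to change.** In SAP 7.9.1.2.1:

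- Start the sum at v = 1 (equivalently, set α_0 = 0).
- Add a common intercept outside the exp(θT_i) factor, so that Y_i0 has the same mean in both arms.
- State that γ_i has mean zero, and give its distribution.
- Show the covariates in the equation, outside the ratio, with the continuous ones centred.

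This costs one index, one added term and two sentences, plus a check that the code matches. If the code already sets α_0 to zero, only the text changes.

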7.9.1.2.2. Assessing Missing at Random (MAR) in MMRM

Sensitivity to departures from the missing-at-random (MAR) assumption will be investigated using a tipping point analysis (Carpenter and Kenward 2013). This method is a sensitivity analysis in multiple imputation under the missing-not-at-random (MNAR) assumption that searches for a tipping point that reverses the study conclusion. Departures from MAR in the solanezumab treatment group will be assessed assuming that participants who discontinue the study have, on average, efficacy outcomes after discontinuation that are worse by some amount δ compared to other similar participants with observed data (ie, compared to a value which would have been assumed under an MAR model). A series of analyses will be performed with increasing values of δ until the analysis conclusion of a statistically significant treatment effect no longer holds. The value of δ that overturns the primary results will represent a tipping point. An interpretation of clinical plausibility of the assumption underlying the tipping point will be provided.

Mean changes from baseline in PACC scores will be analyzed based on data observed while the participant remains on study as well as data imputed using multiple imputation (MI) methodology for time points at which no value is observed. Imputed values in the solanezumab treatment group will first be sampled from an MAR-based multiple imputation model and then δ -adjusted as described below.

Missing-at-random-based imputations will be generated for PACC scores at each time point, and then a value of δ will be added to all imputed values in the solanezumab treatment group prior to analyzing multiply imputed data. This approach assumes that the marginal mean of imputed participant measurements is worse by δ at each time point after discontinuation compared to the marginal mean of participants with observed data at the same time point. Analyses will be conducted with values of δ starting from 0 with increments of 0.10 until the null hypothesis can no longer be rejected. The multiple datasets will be analyzed with the NCS approach described for the primary analysis, and estimated treatment effects will be appropriately pooled.

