- ***Digit-Symbol Substitution Test from the Wechsler Adult Intelligence Scale-Revised (WAIS-R).*** The Digit Symbol Substitution test (Wechsler 1981) is a subset from the WAIS-R. The test consists of small blank squares presented in rows with one of 9 numbers (1-9) randomly printed directly above each blank square. A “key” is printed above the rows of blank squares. The “key” pairs numbers 1 through 9 with an unfamiliar symbol. Following a short series of practice trials, the subject must use the key to fill in the blank squares in order (working from left to right across the rows) with the symbol that is paired with the number over the blank square. The subject must work as fast as possible for 90 seconds. The measure of interest is number of squares filled in correctly within the time limit (maximum raw score = 91). This test engages multiple cognitive abilities including attention, psychomotor speed, complex scanning, visual tracking, and immediate memory.
- ***MMSE Total Score.*** The MMSE (Folstein et al. 1975) is a brief, frequently used screening instrument for Alzheimer’s disease drug studies. The MMSE scale evaluates orientation, memory, attention, concentration, naming, repetition, comprehension, and ability to create a sentence and to copy 2 overlapping pentagons. The MMSE is scored as the number of correctly completed items with a lower score indicative of poorer performance and greater cognitive impairment. The total score ranges from 0 (worse) to 30 (perfect performance).

Each component score is divided by the baseline SD of that component, to form standardized Z-scores. These Z-scores are summed to form the composite, so that a 4-point change on the composite is approximately equivalent to a change of 1 baseline SD on each component.

The administration of the PACC should be recorded (audio only) for quality review purposes according to locally applicable laws and regulations.

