5.1. Primary Objective

The primary objective of this study is to test the hypothesis that solanezumab, administered as an IV infusion every 4 weeks for 4.5 years, will slow cognitive decline as compared with placebo in participants with preclinical AD. The primary objective will be assessed using a constrained Longitudinal Data Analysis (cLDA) Natural Cubic Spline (NCS) analysis (referred to as NCS henceforth) of the primary outcome measure, the Preclinical Alzheimer Cognitive Composite (PACC), a composite that is primarily weighted on episodic memory and executive function tests, in which the specific hypothesis is that the cognitive decline at 240 weeks will be significantly less for solanezumab than for placebo.

The PACC will be composed of 4 components: the total score from the free and cued selective reminding test (FCSRT), the delayed paragraph recall on the logical memory IIa test from the Wechsler Memory Scale, the digit-symbol substitution test from the Wechsler adult intelligence scale-revised, and the MMSE total score. Specifically, for the FCSRT, the total will be the sum of the free and cue score plus the free recall score, resulting in a total from 0 to 96. Each component score is converted to a z-score by subtracting the baseline mean for that component and dividing by the baseline standard deviation for that component. The PACC is the sum of the four resulting z-scores.

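### The tipping-point analysis adds a growing positive δ to imputed solanezumab PACC scores; higher PACC is better, so a significant benefit can never tip

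*SAP*

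**What the plan says.** SAP 7.9.1.2.2 states the intent twice. Solanezumab participants who discontinue are assumed to have "efficacy outcomes after discontinuation that are worse by some amount δ compared to other similar participants with observed data", and the method is said to assume that "the marginal mean of imputed participant measurements is worse by δ at each time point after discontinuation".

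The operation is given separately. After imputation under MAR, "a value of δ will be added to all imputed values in the solanezumab treatment group". The grid and stopping rule are: "Analyses will be conducted with values of δ starting from 0 with increments of 0.10 until the null hypothesis can no longer be rejected". An earlier sentence in the section agrees on the direction of the series: "A series of analyses will be performed with increasing values of δ until the analysis conclusion of a statistically significant treatment effect no longer holds". So δ is zero or positive, it grows, and it is added.

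SAP 5.1 defines the outcome. Each component is "converted to a z-score by subtracting the baseline mean for that component and dividing by the baseline standard deviation", and "The PACC is the sum of the four resulting z-scores". No component is reversed. Protocol 10.1.1 gives the direction of each component: FCSRT counts words recalled (the SAP uses the 0 to 96 total), Logical Memory IIa counts story units recalled (0 to 25), Digit-Symbol counts squares filled correctly (maximum 91), and for the MMSE a "lower score indicative of poorer performance and greater cognitive impairment".

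**The concern.** On a scale where higher is better, making an imputed score worse means taking something away from it. The SAP adds. Read literally, every step of the search gives solanezumab dropouts better cognition than MAR would, so the treatment contrast grows when it should shrink. The search is told to continue until significance is lost, and that cannot happen.

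A second mismatch sits in the same step. The shift applies to every imputed solanezumab value, and values are imputed wherever none was observed. The stated assumption covers only time points after discontinuation. A visit missed by someone still in the study would therefore be shifted too.

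The MMRM, disease progression, completer and per-protocol analyses do not vary the assumption about unobserved outcomes after dropout; this analysis is the one meant to. Coded as written, it could be reported as showing that a positive result survives any departure from MAR.

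**Working it through.** **Planning figure first.** Section 7.9.1.2.2 gives no numerical result, so the scale comes from SAP 6.2: N = 1150 (575 per arm), SD 2.85, 30% attrition, 80% power, two-sided α 0.05, detectable difference 0.532 (0.570 with SD 3.08). SAP 6.2 says the planning assumed an MMRM. The formula is

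MDD = SD × (1.960 + 0.842) × √(2φ/575),

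where φ is the MMRM variance inflation from dropout. With ten post-baseline PACC visits, linear loss to 30% and a common correlation of 0.5 (a value SAP 6.2 gives for the open-label calculation, assumed here for the main period), it gives 0.530 and 0.573. That reproduces the plan's figures closely. A completers-only calculation with 402.5 per arm gives 0.563 and 0.608 and does not.

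**Direction.** All four components score higher for better performance, and the z-scores are summed without a sign change. SAP 7.9.3.2 also treats a positive solanezumab difference as the benefit. Adding δ > 0 to imputed solanezumab values therefore raises the contrast.

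**Size, simple form.** Let f be the share of Week 240 solanezumab values that are imputed. Then contrast(δ) = θ ± fδ. Take θ = 0.532 and f = 0.30. The standard error implied by 80% power is 0.532/2.8016 = 0.190, so the significance bound is 1.96 × 0.190 = 0.372.

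- Subtracting: 0.532 − 0.30δ = 0.372 gives δ = (0.532 − 0.372)/0.30 = 0.53.
- Adding: 0.532 + 0.30δ is above 0.372 for every δ ≥ 0, so there is no solution.

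**Size, with variance that depends on δ.** For a final-visit comparison, SE(δ) = √[2·SD²/(575(1−f)) + f(1−f)δ²/575]. With SD 2.85 and f = 0.30 this is 0.201 at δ = 0.

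| δ | added (as written) | z | subtracted (as intended) | z |
|---|---|---|---|---|
| 0 | 0.532 | 2.65 | 0.532 | 2.65 |
| 0.1 | 0.562 | 2.80 | 0.502 | 2.50 |
| 0.5 | 0.682 | 3.39 | 0.382 | 1.90 |
| 1.0 | 0.832 | 4.12 | 0.232 | 1.15 |
| 2.0 | 1.132 | 5.54 | −0.068 | −0.33 |
| 10 | 3.532 | 12.74 | −2.468 | −8.90 |

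With addition, z tends to √(575 × 0.3/0.7) = 15.7 as δ grows, far above 1.96. No tip appeared for any δ up to 10,000 with SD 2.85 and observed differences of 0.532, 0.563 or 0.75, with SD 3.08 and 0.75, or with f of 0.10, 0.20 or 0.40 (at 0.75 and SD 2.85).

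With subtraction on the SAP's 0.10 grid, the tip is finite every time:

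- SD 2.85, f = 0.30: 0.5, 0.6 and 1.2 for observed differences of 0.532, 0.563 and 0.75.
- SD 3.08, f = 0.30, difference 0.75: 1.1.
- SD 2.85, difference 0.75, f = 0.10, 0.20, 0.40: 3.9, 1.9, 0.9.

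**Cross-check.** One simulated dataset was multiply imputed 30 times and pooled by Rubin's rules. Its estimate was 0.865 (z = 5.09) at δ = 0. Adding δ raised z to 5.26 at 0.1 and 15.08 at 10, with no tip up to δ = 50. Subtracting δ tipped it at 1.8.

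**The case against.** The best reply is that the section makes its direction plain. It says twice that the outcomes are worse by δ and describes a search for the point at which the conclusion is reversed. Only the verb in the operating sentence conflicts, and a programmer who understood the purpose would subtract. Anyone who did code the plus sign would probably notice the estimate improving at the first step, and the loop would produce no tipping value to report. This is fair, and the defect is properly described as a contradiction between intent and operation. But the operating sentence is the one that gets coded, the words about increments and increasing values leave no room for a silently negative δ, and nothing elsewhere in either document settles the sign.

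Three narrower points stand as qualifications. First, the failure to tip is conditional: a non-significant primary result ends the search at δ = 0, and a result significantly favouring placebo would be moved toward the null. Second, any single tipping value is illustrative. Third, how often visits were missed by participants still in the study is unknown. SAP 6.1 says the pandemic hiatus let people pause without missing visits, so the pandemic need not have created many such gaps. With the sign corrected, shifting those gaps as well would be the more conservative choice. The mismatch between all imputed values and time points after discontinuation remains in the text regardless.

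**Conclusion.** The concern holds. As written, SAP 7.9.1.2.2 improves imputed solanezumab outcomes by δ while claiming to worsen them. If the primary result significantly favours solanezumab, the case the analysis is built for, no tipping point exists. At 30% imputed, each 0.10 step moves the contrast about 0.03 points the wrong way.

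The direction rests only on the scoring of the PACC and the wording of the operating step. The sizes rest on assumptions: 30% of Week 240 values imputed, δ applied to all of them, and a final-visit comparison standing in for the full spline model. On those terms the intended tip is about 0.5 for an observed 0.532. Across the scenarios tried it runs from 0.5 to 3.9.

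**What to change.** In SAP 7.9.1.2.2:

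- State that δ is subtracted from the imputed solanezumab PACC values, or equivalently that the added values run 0, −0.10, −0.20 and so on.
- Apply the shift only at time points after study discontinuation, and leave values missed by participants still in the study at their MAR imputations, as the section's own assumption implies.
- Retitle the section. It names the MMRM, but the imputed datasets are analysed with the NCS primary model. This part is editorial.

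The cost is one or two sentences of SAP wording plus the heading, with no additional data. The correction should be recorded in writing before the analysis is run.
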